1.2. Secondary Objectives/ Endpoints

- A. To determine the objective response rate (ORR) using immune related Response Criteria (irRC) to nivolumab and ipilimumab when administered in combination to patients with pre-treated advanced NSCLC who have experienced primary resistance to anti-PD-1 axis therapy as their last line of systemic therapy.
- B. To determine progression-free (RECIST v1.1 and irRC) and overall survival with nivolumab and ipilimumab when administered in combination to patients with pre-treated advanced NSCLC who have experienced primary resistance to anti-PD-1 axis therapy as their last line of systemic therapy.
- C. To determine ORR and progression free survival (PFS) by RECIST v1.1 and irRC, and overall survival, in patients with pre-treated advanced NSCLC who have experienced acquired resistance to anti-PD-1 axis therapy as their last line of systemic therapy
- D. To characterize the safety profile of nivolumab and ipilimumab when administered in combination, and feasibility of sequential biopsies, in patients with pre-treated advanced NSCLC who have experienced primary or acquired resistance to anti-PD-1 axis therapy as their last line of systemic therapy
- E. To evaluate changes in the tumor microenvironment and blood after adding ipilimumab to anti- PD-1 axis therapy in patients with primary and acquired resistance to anti-PD-1-axis as their last line of systemic therapy

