4.1.1. Tumor Biopsies and Pharmacodynamic Blood Draws

A trial tumor biopsy will be required of all enrolled patients before starting treatment. A second mandatory tumor biopsy will be performed between day 56 and 70 of trial therapy (9-10 weeks after initiation of therapy). These on-trial tumor biopsies must be collected via core, forceps, or incision/ excision. Although the second biopsy will generally be obtained from the same site as the first one, there may be circumstances when another tumor site would alternatively be biopsied (e.g. lesion initially biopsied becomes too small to safely and/or effectively biopsy).

Optional biopsies may be performed at sites of response (including partial response, or stable disease at least 24 weeks) or progression while on treatment. We anticipate that such biopsies will help to characterize changes in the tumor immune microenvironment that play a role in mitigating response or resistance to treatment, respectively.

If archived tumor tissue from a biopsy performed prior to enrollment is available, unstained slides or block will be requested for additional analysis of biomarkers (as consented to in the informed consent document).

Blood draws to characterize the peripheral anti-tumor immunologic milieu will be collected prior to the initiation of combination therapy. Serial draws will be performed 2 weeks, 4 weeks, 6 weeks, and 9 weeks after the initiation of therapy (should correspond with timing of on-treatment biopsy) as well as at the time of disease progression.

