5.2. On-Study Visits

The day of the nivolumab infusion (every 2 weeks) and the day of the ipilimumab infusion (every

6 weeks):

- 1) History and physical examination
- 2) Measurement of height, weight and vital signs (including blood pressure, heart rate, respiratory rate, oxygen saturation, and temperature).
- 3) Performance status evaluation
- 4) Review concomitant medications
- 5) Adverse events assessment
- 6) CBC with differential, serum chemistry (Na, K, Cl, CO₂, BUN, creatinine, glucose, calcium), magnesium, phosphate, liver function tests (albumin, total protein, alkaline phosphatase, total and, ALT, AST), LDH
- 7) Pregnancy test (serum or urine) for women of childbearing potential (every 6 weeks)
- 8) Administration of nivolumab and/or ipilimumab accordingly.
- 9) TSH with reflex free T4 and free T3 (every 6 weeks)

Tumor response assessment will occur every 9 weeks after initiating trial therapy for the first 24 weeks, and thereafter every 12 weeks.

Tumor biopsies (excision, core or forceps) will be performed 9 to 10 weeks after initiating trial therapy after the 4th or 5th nivolumab infusion to allow for analysis of pharmacodynamics changes related to trial therapy (see Sections 4.1.1 and 7). Blood will be drawn for correlative studies the day of the first four nivolumab infusions, and the week after the 5th nivolumab infusion.

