7. CORRELATIVE/SPECIAL STUDIES

Correlative studies will be conducted on serial tumor biopsy and blood specimens. All patients will undergo a tumor biopsy prior to initiation of trial therapy, and after their 5th treatment with nivolumab (study week 10). Blood will be drawn prior to each tumor biopsy to allow additional correlative studies.

Tissue from Serial Tumor Biopsies:

- a. Multiplexed quantitative immunofluorescence will be used to evaluate multiple markers on tumor/ immune cells, including, but not limited to, PD-L1, PD-1, CK, CD4, CD8, CD20, Ki67, granzyme B, and IDO1.
- b. RNA, TCR and DNA sequencing (with neoantigen analysis)
- c. Additional studies, depending on tissue availability, may include: functional T cell studies (neoantigen stimulation assay, T cell culture) and generation of patient derived xenografts.

Serial Blood Draws:

- a. Mass cytometer (CyTOF 2, DVS Sciences) will be used to comprehensively characterize phenotypic (CD45, CD3, CD8, CD4, CD33, CD11b, CD123, CD56, CD16, CD20, CD66b, CD68, TBET, GATA-3, FOXP-3, CD14, CCR7, CD45RA, $\gamma\delta$ TCR) and functional (KI-67, HLA-DR, CD25, PD-1, CD80, CD16, IFN γ , TNF α , Granzyme B, Caspase 3, PARP) changes of blood cells in relation to changes in tumor tissue.
- b. Tetramer staining using neoantigenic peptides or ELISPOT (neoantigen stimulation assay).

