9. STATISTICAL CONSIDERATIONS

This trial is designed to determine the objective response rate (ORR) using RECIST v1.1 and irRC to nivolumab and ipilimumab when administered in combination to patients with advanced NSCLC and primary resistance to PD-1 axis inhibitor therapy. Details on the response criteria and its duration are described in Section 8 of this protocol. For our primary endpoint we will employ a Simon two-stage design. This design is based on our intuition for a very low response rate and not on any specific experimental evidence. The study design will terminate early if there are no responses or prolonged stability (≥ 24 weeks) using irRC among the first 10 patients enrolled. Otherwise we will enroll a maximum of 40 and reject the null hypothesis if we observe 4 or more

positive responses. For a null hypothesis with a 5% ORR and alternative with a 19% ORR, this criterion has significance level 0.1 and power greater than 85%. The null and alternative hypothesis rates are not motivated by experimental evidence but rather, are examples of one pair of hypotheses that can be tested using this design.

An operating characteristic of this design with other ORRs is plotted here:

We anticipate enrollment at a rate of at least 2 patients per month. Patients who drop out or leave the study before receiving any experimental treatment will be replaced. Patients who leave the study after receiving any study treatment will be considered as treatment failures and not be replaced.

Our secondary analyses correlate ORR, time-to-event measures and correlative metrics listed in Section 7. Specifically, duration of response, progression-free survival (PFS) and overall survival (OS) will be estimated along with the corresponding 95% CI, plotted using the Kaplan-Meier method. These plots will also be prepared separately by RECIST v 1.1 criteria and irRC and tested using the log-rank test. Duration of response, OS, and PFS are defined in Section 8.

Marker data and other metrics listed in Section 7 will be correlated to ORR and PFS using Cox proportional hazard regression methods. These values will be analyzed marginally using heatmaps and single linkage to identify any subpopulations.

The following analysis sets will be defined in this trial:

- Full Analysis Set: All subjects who receive at least 1 dose of any trial treatment.

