- Completer Analysis Set: All subjects who complete the trial, all scheduled treatments, all biomarker assessments, and all tumor assessments.
- Safety Analysis Set: All subjects who receive at least 1 dose of any trial treatment but subsequently drop out of the study for any reason.
- Correlative Biomarker Set: All subjects who receive at least one dose of any trial treatment and have at least one set of correlative marker data listed in Section 7.

No formal statistical ORR analyses will be conducted on the 10 additional patients with acquired

resistance, though the finding of immune related response in 1 or more patients would be unexpected, and should prompt further study.

Demographics and baseline laboratory results will be summarized by cohort (primary and acquired resistance to anti-PD-1 axis therapy) and by all patients using descriptive statistics.

Safety analysis will be performed in all treated subjects. Descriptive statistics of safety will be presented using National Cancer Institute (NCI) Common Terminology Criteria for Adverse Events (CTCAE) version 4.0 by cohort (primary and acquired resistance to anti-PD-1 axis therapy) and by all patients. All on-study AEs, drug-related AEs, SAEs and drug-related SAEs will be tabulated using worst grade per NCI CTCAE v 4.0 criteria by system organ class and preferred term. On-study lab parameters including hematology, coagulation, chemistry, liver function and renal function will be summarized using worst grade per NCI CTCAE v 4.0 criteria.

References:

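### Section 9 does not say which marker samples enter the Cox model for PFS: on-treatment values can post-date the week-9 events they are meant to explain, and no method is stated for the pre/post change

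*Combined protocol and SAP*

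**What the plan says.** - **Model.** Section 9: "Marker data and other metrics listed in Section 7 will be correlated to ORR and PFS using Cox proportional hazard regression methods". It adds heatmaps and single-linkage clustering. It has no baseline-only restriction, landmark, delayed entry or time-dependent covariate.
- **Outcome clock.** Section 8 times PFS from the first nivolumab dose. Section 5.2: "Tumor response assessment will occur every 9 weeks after initiating trial therapy for the first 24 weeks". The calendar (5.4) puts the first on-study scan in week 9.
- **Second biopsy.** Section 4.1.1 places it "between day 56 and 70 of trial therapy (9-10 weeks after initiation of therapy". Section 5.2 also gives 9 to 10 weeks, but "after the 4th or 5th nivolumab infusion". Section 7: "All patients will undergo a tumor biopsy prior to initiation of trial therapy, and after their 5th treatment with nivolumab (study week 10". The calendar shows week 10.
- **Other on-treatment samples.** Section 4.1.1 has blood at 2, 4, 6 and 9 weeks and again at progression, and optional biopsies at sites of response or progression.
- **Objective.** Section 1.2, objective E: "To evaluate changes in the tumor microenvironment and blood after adding ipilimumab".
- **Analysis set.** The Correlative Biomarker Set needs one dose of treatment and patients who "have at least one set of correlative marker data listed in Section 7". A pre/post pair is not required.

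**The concern.** A Cox model with time from first dose treats each covariate as known at time zero. A second-biopsy value is not known then. On the calendar's order, a patient whose progression is dated at the week-9 scan is biopsied the following week, after the event. If tissue from a tumor that is already growing differs from tissue from one that is not, the marker carries information about an outcome that has already occurred, and the model reads this as prognosis. Patients who die or stop before the biopsy have no value, so missingness also depends on the outcome. Samples triggered by progression are the extreme case.

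The serial biopsies are mandatory, and the protocol presents them as the way to examine its mechanistic hypothesis. At stake are a false prognostic claim from those samples and the absence of any stated analysis for the change they were collected to measure.

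**Working it through.** The plan gives no power, event count or sample size for the marker analysis, so it has no figure to reproduce.

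**Step 1: order of scan and biopsy.** With day 1 as first dose, the 5th nivolumab falls on day 1 + 4 × 14 = 57, the first day of week 9. Week 9 is days 57 to 63 and week 10 is days 64 to 70. Day 56 is therefore the last day of week 8, before the 5th infusion. On the calendar and in Section 7 the biopsy follows the week-9 scan. On 4.1.1 and 5.2 it can come just before or after it. Blood at weeks 2, 4 and 6 precedes the first scheduled scan; the week 9 to 10 draw and the progression draw do not reliably do so.

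**Step 2: how many patients have the event by the week-9 scan.** Assume exponential PFS with median m months. The share is 1 − 2^(−(63/30.44)/m), where 63/30.44 = 2.07.

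| Median PFS | Source | Share by week 9 | Of 40 |
|---|---|---|---|
| 3.9 months | Table 2.2.2, same regimen, first line | 1 − 2^(−0.531) = 31% | 12 |
| 2.6 months | lower 95% limit, same table | 1 − 2^(−0.796) = 42% | 17 |
| 2.0 months | assumed | 1 − 2^(−1.035) = 51% | 20 to 21 |

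A 60% share, the upper end used below, corresponds to a median of about 2.07/1.32 = 1.6 months (assumed). The first-line population had not failed PD-1 axis therapy, so a share above 31% is plausible here, but the documents do not give one.

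**Step 3: false-positive rate.** Simulation with 40 patients, 600 to 1,000 replicates per setting, and progression read at weeks 9, 18, 30 and every 12 weeks after. The marker has no effect on later hazard but is shifted by 0.5 or 1.0 SD (assumed) in patients already progressed at week 9. Two-sided 5% test.

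| Model, and week-9 progressors with a biopsy | Week-9 share | Shift 0.5 SD | Shift 1.0 SD |
|---|---|---|---|
| Cox from first dose, all | 31% | about 12 to 14% | 38% |
| Cox from first dose, all | 40 to 60% | 17 to 21% | 50 to 62% |
| Cox from first dose, half | 40 to 60% | 8 to 12% | 24 to 40% |
| Cox from first dose, a quarter | 40 to 60% | 6 to 7% | 12 to 18% |
| Landmark after the week-9 scan | 31 to 60% | 2 to 5% | 2 to 5% |

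With no shift, Cox from first dose rejects in 3 to 5%. With every progressor biopsied, the median hazard ratio in the shifted settings is about 0.70 to 0.87 per SD, where the true value for later PFS is 1.0. The biopsied fractions are assumptions.

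**Step 4: price of the landmark.** Patients left after week 9: 40 × 0.69 = 28, 40 × 0.60 = 24, 40 × 0.40 = 16. For a true hazard ratio of 0.7 per SD, power is about 14 to 32% with 16 to 24 patients.

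**Step 5: objective E.** Section 9 offers the Cox model, heatmaps and clustering. It gives no change score, paired test or set of patients with both samples.

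**The case against.** Section 9 nowhere says that second-biopsy values go into the PFS model. A reader might infer that the plan prescribes this; it does not. A baseline-only reading is open, and the defect is an unspecified time point. That stands, and it makes the finding conditional. It does not remove it, because the sentence covers everything in Section 7, including both biopsies and serial blood.

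The inflation comes entirely from the assumed shift. The documents do not support one, and a difference at week 10 could be a cause of progression as well as a result. So the model can mislead; it need not.

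Not every early progressor will be biopsied: progression ends treatment and study participation (4.4, 4.5) unless the exception in 4.6 applies. This lowers the false-positive rate, as the half and quarter rows show, but it replaces part of the bias with outcome-dependent missing data.

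A reader might also infer that change is not going to be examined at all. That goes too far. Section 7 speaks of changes in blood cells in relation to tumor changes, although as an assay description, and the Completer Analysis Set requires all biomarker assessments, although it is not tied to objective E. What is missing is a stated statistical method.

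Finally, this is a secondary objective with no decision rule, and the primary ORR test is untouched. That limits the weight of the point, but the biopsies are mandatory and deserve an analysis that can answer their question.

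**Conclusion.** The point holds in conditional form. Section 9 leaves the marker time point open. If on-treatment values are used in the model as written, roughly 12 or more of 40 patients (31% at the first-line median, more at shorter medians) would have their PFS event dated at or before the second biopsy. The false-positive rate at a nominal 5% would then be about 12 to 62% if all of them are biopsied and about 6 to 40% if a quarter to a half are. These figures rest on the assumed 0.5 to 1.0 SD shift, exponential PFS and week-9 shares of 31 to 60%; with no shift the rate is about 5%.

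The documents do not support the wider inference that every marker result for PFS is invalid. Baseline markers are unaffected, and patients who progress after the second biopsy have the marker first. Separately, objective E has no stated method, and its analysis set admits patients with a single sample.

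**What to change.** In Section 9:

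- (a) Relate PFS and OS from first dose to baseline markers only.
- (b) Analyse on-treatment values or changes from the sample date among patients alive and progression-free then, or as time-dependent covariates. Exclude samples triggered by progression from the PFS model.
- (c) Make the within-patient change, in patients with both samples, the analysis of objective E: paired signed-rank test and median change with confidence interval, by cohort. Report how many patients lack a pair, and why.

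Reconcile the second-biopsy timing in 4.1.1, 5.2, the calendar in 5.4 and Section 7. No particular window is needed for (a) to (c) to work.

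The change is mainly wording, but the landmark has a real cost that the plan should disclose. It keeps only about 16 to 28 of 40 patients, has low power, and omits early progressors, who matter most for a question about resistance. They stay in the paired analysis if they have both samples.

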4. TREATMENT PLAN

4.1. Study Design

This is a phase II study employing a 2-stage design to evaluate the primary endpoint of ORR to combination therapy with nivolumab 3 mg/kg administered intravenously (IV) every 2 weeks with ipilimumab 1 mg/kg administered IV every 6 weeks in patients with advanced NSCLC and primary resistance to anti-PD-1 axis therapy. If there is at least 1 response or prolonged stability (≥ 24 weeks) using irRC appreciated in the first 10 patients who initiate trial therapy, an additional 30 patients will be enrolled to a total of 40 patients. An additional 10 patients with acquired resistance to anti-PD-1 axis therapy will be enrolled in an exploratory cohort receiving the same therapy.

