4.5. Criteria for Removal from Study

Patients will be removed from study when any of the criteria listed in Section 4.4 applies. The reason for study removal and the date the patient was removed must be documented.

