6. ADVERSE EVENTS: LIST AND REPORTING REQUIREMENTS

6.1 Safety Analysis

Safety will be analyzed for patients treated in this study. All patients who receive any amount of study drug will be evaluable for toxicity.

At each visit, a brief focused history will be obtained and any indication of treatment-related toxicity will be evaluated by appropriate examination and/or laboratory/radiographic studies.

Safety analyses will include summaries of adverse event rates and changes in laboratory results, as well as number of CTCAE (v4.0) toxicity grades for both laboratory and non-laboratory data.

The evaluation period should extend from date of first treatment until 100 days from discontinuation of treatment, and until resolution from all acute toxicities associated with the drug administration.

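### The Safety Analysis Set is defined as treated subjects who later drop out, which conflicts with the all-treated safety population stated elsewhere

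*Combined protocol and SAP*

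**What the plan says.** The list of analysis sets in Section 9 gives the Safety Analysis Set as "All subjects who receive at least 1 dose of any trial treatment but subsequently drop out of the study for any reason". In the same list the Full Analysis Set opens with the same words but has no such clause: "Full Analysis Set: All subjects who receive at least 1 dose of any trial treatment". A separate Completer Analysis Set holds subjects who finish the trial with all their treatments and assessments.

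The safety population is described in three other places. Section 6.1 states "Safety will be analyzed for patients treated in this study" and then "All patients who receive any amount of study drug will be evaluable for toxicity". Further on in Section 9, the paragraph that specifies the adverse event and laboratory tables begins "Safety analysis will be performed in all treated subjects".

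The objective these analyses serve is item D of Section 1.2, "To characterize the safety profile of nivolumab and ipilimumab when administered in combination", in patients with primary or acquired resistance. It is not restricted to patients who leave the study.

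**The concern.** A safety population normally contains everyone exposed to study drug. The named set adds a second condition, that the subject later drops out. A patient who is treated and remains on study would be missing from it, along with that patient's adverse events.

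The condition is also related to the outcome. Section 4.4 lists unmanageable toxicity among the reasons to stop treatment, and Section 4.5 makes each of those reasons a ground for removal from study. A set restricted to patients who left is therefore selected partly on a possible consequence of the events being counted. If a programmer built the safety tables from the list of named sets, both the numerators and the denominators could be wrong.

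**Working it through.** The plan gives no figure to reproduce here, so the check compares the statements of the safety population.

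| Place | Population | Drop-out condition |
|---|---|---|
| Section 6.1, first sentence | patients treated (the word all is not used) | none |
| Section 6.1, second sentence | all who received any amount of drug | none |
| Section 9, safety-table paragraph | all treated subjects | none |
| Section 9, Safety Analysis Set | at least 1 dose and later dropped out | yes |

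Of four statements, 3 have no drop-out condition and 1 does. The name Safety Analysis Set appears once in the documents, in its own definition.

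Let T be the subjects given at least one dose and D those who drop out.

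- Full Analysis Set = T.
- Safety population in the three other statements = T.
- Safety Analysis Set as defined = T ∩ D.

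T ∩ D equals T only if every treated subject counts as a drop-out. Whether that can happen depends on what dropping out means, and the documents do not define it.

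**Narrow reading (withdrawal or early departure).** T ∩ D is smaller than T whenever any treated subject stays. In ordinary usage a subject who completes the trial has not dropped out, so the Safety and Completer sets would have no member in common. This contradicts the other three statements and does not fit objective D.

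**Broad reading (any removal from study).** Section 4.5 says "Patients will be removed from study when any of the criteria listed in Section 4.4 applies", and those criteria include progression, death and study termination. By the end of the study T ∩ D could approach T. The clause then does no work, and the set is the Full Analysis Set under another name.

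The clause is thus contradictory on one reading and redundant on the other.

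If both cohorts fill, 40 + 10 = 50 patients are treated. The number of them in D cannot be derived, because the documents give no drop-out rate. Nor do they say how adverse event rates would differ between those who leave and those who stay. Neither the size nor the direction of any bias can be calculated.

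**The case against.** The strongest reply is that the plan already gives the right instruction. The paragraph that sets out the safety tables says they cover all treated subjects, Section 6.1 agrees, and no table is assigned to the Safety Analysis Set by name. An analyst who follows the safety plan as written would use the correct population, so the selection problem arises only if someone programs from the list of sets. This stands, and it is the main reason the point is minor.

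A second reply is that treatment is open-ended and removal covers progression, death and study termination, so every treated subject might eventually qualify. That reading is possible but not secure. The replacement rule in Section 9 names dropping out and leaving the study as alternatives, which suggests that dropping out may be the narrower term, and a Completer set makes sense only if some subjects complete. Even if the broad reading is accepted, the clause serves no purpose.

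A third reply is that the count of three against one is a tally of wording. Two of the three are consecutive sentences, and one of those lacks the word all. This is fair: the count shows where the text disagrees and does not measure harm. It is also true that the drafter's intention is not documented; the clause may have been meant to say that drop-outs are included.

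**Conclusion.** The concern holds, as a minor point. The formal definition of the safety population, read literally, conflicts with the three other statements of that population and with the unrestricted safety objective. It is probably a drafting slip, though that is inference from the surrounding text. The practical effect is limited as long as the safety tables follow the paragraph that specifies them. No bias estimate is offered, because the documents do not supply the inputs. The conclusion rests only on the wording of the definition and on dropping out being undefined. The primary endpoint, the stage-1 rule and the sample size are not affected.

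**What to change.** Delete the drop-out clause, so that the Safety Analysis Set consists of all subjects who receive at least one dose of any trial treatment. Add one sentence stating that the set is then identical to the Full Analysis Set and that all safety tables use it. If the clause was meant to make clear that drop-outs are kept, say that they are included. The cost is one deleted clause and one added sentence, with no new data and no effect on the design.

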| 
Statistical Methods:
 
For the primary endpoint of objective response rate (ORR) by RECIST v1.1 among patients with primary resistance to anti-PD-1-axis therapy, a Simon two-stage design will be employed. The design is based on our intuition for a very low anticipated response rate and not on any specific experimental evidence. The study will terminate early if there are no responses or prolonged stability (≥ 24 weeks) using irRC among the first 10 patients enrolled. Otherwise we will enroll a maximum of 40 patients with primary resistance and reject the null hypothesis of no objective response if we observe 4 or more positive responses. For a null hypothesis with a 5% ORR and alternative with a 19% ORR, this criterion has significance level 0.1 and power greater than 85%. The null and alternative hypothesis rates are not motivated by experimental evidence but rather, are examples of one pair of hypotheses that can be tested using this design.
 
Progression-free survival will be estimated with derivation of the corresponding 95% CI, plotted using the Kaplan-Meier method. Overall survival will be plotted using the Kaplan-Meier method.
 |

Time-to-event endpoints (PFS, OS) will be analyzed using the Kaplan-Meier plots. We will correlate OSS and PFS with ORR using Cox proportional hazards regression methods. No formal statistical analyses will be conducted on the 10 additional patients with acquired resistance, though the finding of immune related response in 1 or more patients would be unexpected, and should prompt further study.

Funding, Regulatory, and Feasibility Issues:

- Ipilimumab and nivolumab will be supplied by Bristol Myers Squibb Company.
- Bristol Myers Squibb Company will provide additional trial funding, including funding of serial biopsies.
- IND for trial therapy to be held by [name].

Patient Acceptability/Ethics and Consent Issues:

None anticipated

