3. PATIENT SELECTION

3.1. Inclusion Criteria

- A. Signed Informed Consent
- B. Ability to comply with the protocol
- C. Age \geq 18 years
- D. Histologically or cytologically documented, locally advanced or metastatic (i.e., Stage IIIB not eligible for definitive chemoradiotherapy, Stage IV, or recurrent) NSCLC (per the American Joint Committee /AJCC staging system)

- E. ECOG performance status of 0 to 2
- F. Measurable disease, as defined by RECIST v1.1. Previously irradiated lesions can be counted as target lesions if clearly progressing after radiation.
- G. Chemotherapy-naive and treated patients will be eligible, with no limit on number of prior therapies. Patients with NSCLC known to harbor an ALK rearrangement, or EGFR mutation known to be sensitive to FDA-approved tyrosine kinase inhibitors (TKI), are only eligible after experiencing disease progression (during or after treatment) or intolerance to an FDA approved EGFR TKI or ALK TKI, respectively.
 - a. Patients with TKI-treated EGFR mutant NSCLC harboring the secondary EGFR T790M tumor must have received prior osimertinib
 - b. Patients with crizotinib-treated ALK rearranged NSCLC must have received a next generation ALK inhibitor (e.g. ceritinib, alectinib or brigatinib)
- H. Prior palliative radiotherapy must have been completed at least 2 weeks before the first dose of study drug.
- I. Anti- PD-1 Axis therapy (anti-PD-1 or anti-PD-L1, e.g. nivolumab, pembrolizumab, atezolizumab, durvalumab, avelumab) must be the most recent systemic anti-tumor treatment received in all patients, with documented progressive disease. Last administration of anti-PD-1 axis therapy must have been at least 3 weeks before the first dose of study drug.
 - a. Patients to be enrolled to the primary cohort (primary resistance) must have had progressive disease or stable disease less than 24 weeks as the best clinical response to anti-PD-1-axis monotherapy
 - b. Patients to be enrolled to the exploratory cohort (acquired resistance) must have had stable disease for at least 24 weeks, partial response, or complete response as the best clinical response to anti-PD-1-axis monotherapy, with subsequent progression of disease
- J. At least one tumor amenable to incisional, excisional, core or forceps (transbronchial) biopsy. Patients must be willing to undergo tumor biopsies before starting trial therapy, and 9 to 10 weeks after initiation of therapy.

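### Acquired-resistance cohort: does calling one or more responses in ten patients unexpected need an assumed rate and a confidence interval?

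*Combined protocol and SAP*

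**What the plan says.** Section 4.1 adds 10 patients with acquired resistance as an exploratory cohort on the same therapy. Section 3.1 defines them by what happened on earlier monotherapy: stable disease for at least 24 weeks, "partial response, or complete response as the best clinical response to anti-PD-1-axis monotherapy, with subsequent progression of disease".

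The synopsis (Statistical Methods) states: "No formal statistical analyses will be conducted on the 10 additional patients with acquired resistance". Section 9 carries the same exclusion but limits it to ORR. Both then say that "the finding of immune related response in 1 or more patients would be unexpected, and should prompt further study".

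Secondary objective C in Section 1.2 covers this cohort: "To determine ORR and progression free survival (PFS) by RECIST v1.1 and irRC, and overall survival, in patients with pre-treated advanced NSCLC". Section 8 defines objective response as confirmed complete or partial response, counts patients without a post-baseline assessment as non-responders, and has response data listed for every patient and summarised.

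The only response rates in the statistical plan are for the primary-resistance cohort: "For a null hypothesis with a 5% ORR and alternative with a 19% ORR". The plan says that these are examples that do not rest on data. For intervals, Section 9 says that duration of response, PFS and "overall survival (OS) will be estimated along with the corresponding 95% CI"; ORR is not in that list.

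**The concern.** A statement in a statistical section that a result would be unexpected invites the question of how improbable it is, and under what rate. The plan gives neither for this cohort. The eligibility definition describes response to earlier monotherapy and says nothing about the response rate to the combination. The low expectation expressed elsewhere concerns the primary-resistance cohort, including the synopsis phrase "reject the null hypothesis of no objective response if we observe 4 or more positive responses", which sits beside a null rate of 5%.

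If 5% is carried across, the supposedly unexpected event happens about two times in five. The sentence is also the plan's only guide to reading the response part of objective C, and no interval accompanies it. The risk is that a single response among ten is presented as a surprising signal when it is compatible with a very wide range of true rates.

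**Working it through.** **Inputs.** Cohort size n = 10 (Section 4.1). Trigger: 1 or more immune-related responses (Section 9). True rate p: not given, so a range is assumed. The 5% and 19% are borrowed from the primary-resistance cohort (Section 9).

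**1. The plan's own figures.** There is no probability or rate for this cohort to reproduce. The source of the borrowed 5% can be checked. Take the primary rule as stop if 0 of 10 respond, otherwise reject if 4 or more of 40 respond, and count only responses at stage 1:

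P(reject) = Σ over x = 1 to 10 of P(X₁ = x) × P(X₂ ≥ max(4 − x, 0)), with X₁ ~ Bin(10, p) and X₂ ~ Bin(30, p).

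- p = 5%: 0.1018, against a stated significance level of 0.1 (agrees after rounding).
- p = 19%: 0.857, against stated power above 85% (agrees).

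So the 5% and 19% describe that design and that cohort.

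**2. Chance that the trigger is met.** P(X ≥ 1) = 1 − (1 − p)^10.

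| Assumed true rate p | P(0 of 10) | P(1 or more of 10) |
|---|---|---|
| 1% | 90.4% | 9.6% |
| 3% | 73.7% | 26.3% |
| 5% | 59.9% | 40.1% |
| 10% | 34.9% | 65.1% |
| 19% | 12.2% | 87.8% |

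At 5% the expected count is 10 × 0.05 = 0.5 and the single most likely count is zero.

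**3. Rate below which the word would fit.** If *unexpected* means a chance of at most c, then p must be at most 1 − (1 − c)^(1/10).

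| Meaning given to *unexpected* (c) | Largest p |
|---|---|
| 5% | 0.51% |
| 10% | 1.05% |
| 20% | 2.21% |
| 50% (less likely than not) | 6.70% |

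The plan sets no c. On the everyday meaning in the last row, the word is consistent with 5%.

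**4. Interval a report would show.** Clopper-Pearson 95%, n = 10.

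| Responses | 95% CI |
|---|---|
| 0 | 0% to 30.8% |
| 1 | 0.25% to 44.5% |
| 2 | 2.5% to 55.6% |

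The interval for 1 of 10 contains both 5% and 19%. That shows how imprecise ten patients are. It does not show that a response was likely beforehand; a result can be both surprising and imprecise.

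**5. What depends on the word.** With or without *unexpected*, further study is prompted at one response and not at zero. Stage 1 of the primary cohort uses a similarly low bar: "at least 1 response or prolonged stability (≥ 24 weeks) using irRC appreciated in the first 10 patients". No test, sample size or stopping decision depends on the adjective.

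**The case for a change.** The best case for an edit is that it is cheap and would be made before results are known. It could drop the unsupported adjective, commit to an exact interval for ORR by both criteria, and bring the synopsis (which excludes all formal analyses of this cohort) into line with Section 9 (which excludes only ORR analyses). It would also remind readers that zero of ten does not exclude rates up to 30.8%.

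Much of this is true as description. No rate is given, no ORR interval is promised, and the two exclusions differ in scope. The sentence also does not say whether prolonged stability counts as an immune-related response; if it did, the chances above would be higher. What does not follow is that anything would come out differently:

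- Section 8 and Appendix 4 already supply a working reading, namely confirmed irCR or irPR.
- Section 9 is the fuller statement on the exclusion, and an analyst would follow it.
- The interval is computed from the reported count alone, and no decision depends on which interval method is used.
- Printing 5%, 10% or 19% in the sentence would attach rates to this cohort that have no support for it.
- The missing ORR interval is not particular to this cohort, since Section 9 states none for the primary cohort either.

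**Conclusion.** No change to the plan is needed. The word *unexpected* has no stated rate behind it, but nothing in the documents shows it to be wrong. The 40.1% figure rests entirely on borrowing 5% from a different cohort and a different response criterion. Over assumed rates of 1% to 10% the chance runs from 9.6% to 65.1%, and at 5% a zero count is still the more likely outcome. The one-response trigger is a fair choice for an exploratory cohort of ten in which no hypothesis is tested, and it works identically without the adjective.

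The absent ORR interval is a reporting detail that analysts will fill sensibly when they report objective C, and the differing scope of the exclusion is a clerical mismatch. The calculations assume independent patients with a common response rate, and that only confirmed responses count. The primary endpoint, its error rates and the stage 1 rule are not touched.
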